Number Planned	132 subjects are to complete this study: all in the treatment arm. Each patient will have at least one injured organ and their other organs will serve as controls compared to the other study subjects. Any subjects who do not complete the study will not count toward this number.
Major Inclusion Criteria	
 Age 8 to 17 years inclusive Abdominal solid organ injury visualized on computerized tomography Hemodynamically stable

October 16, 2019

Confidential

Name of Sponsor	[name], MPH
Coordinating Center	Boston Children's Hospital
Investigational Product	Lumason
ASSESSMENTS	
Efficacy	Lumason will be considered efficacious if $\geq 90\%$ of the abdominal solid organ injuries identified on computerized tomography are able to be visualized on contrast enhanced ultrasound.
Pharmacokinetics and Pharmacodynamics	No pharmacokinetics or pharmacodynamics will be performed.
Safety	Study subjects will be monitored for the development of any adverse reactions for 30 minutes following the final infusion of Lumason. No laboratory or other imaging studies are planned.
STATISTICAL METHODS AND ANALYSIS	
Efficacy	Lumason will be considered efficacious if $\geq 90\%$ of the abdominal solid organ injuries identified on computerized tomography are able to be visualized on contrast enhanced ultrasound.
Pharmacokinetics and Pharmacodynamics	No pharmacokinetics or pharmacodynamics will be performed.
Safety	Study personnel will monitor subjects for 30 minutes following the last infusion of Lumason. Patients will be maintained on a cardiopulmonary monitor through this time period. All adverse events will be graded according to the criteria specified by the Common Terminology Criteria for Adverse Events (CTCAE) Version 4.03 (NIH, June 14, 2010).

TABLE OF CONTENTS

	Page
ABBREVIATIONS AND DEFINITIONS	7
1. BACKGROUND	8
1.1 Name and Description of Investigational Product	9
1.2 Results of Nonclinical Studies	10
1.3 Results of Clinical Studies	10
2. STUDY OBJECTIVES.....	11
3. INVESTIGATIONAL PLAN.....	12
3.1 Overall Study Design and Plan	12
3.1.1 Study Endpoints	12
3.2 Discussion of Study Design, Including Choice of Control Groups	13
3.3 Selection of Study Population.....	13
3.3.1 Inclusion Criteria	14
3.3.2 Exclusion Criteria	14
3.3.3 Removal of Subjects from Therapy or Assessment.....	14
3.3.3.1 Subject Withdrawal or Early Termination	15
3.3.3.2 Planned Follow-up for Discontinued Subjects.....	15
3.4 Study drug.....	15

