1.3 RESULTS OF CLINICAL STUDIES

Preliminary Studies

Several European trials have investigated the use of CEUS to identify abdominal solid organ injuries seen on CT in children. These studies have used SonoVue, which is the European brand-name of Lumason. Sessa reported a retrospective series of 254 adults and children aged from 7

to 82 who underwent ultrasound, CEUS using SonoVue and CT to evaluate their abdomen after injury. 84 abdominal injuries were noted on CT, 50 of which were seen on ultrasound. The use of CEUS allowed the visualization of 81 of 84 injuries with no adverse events related to contrast administration (9).

Valentino et al reported a prospective study of the sensitivity and specificity of ultrasound and CEUS (CEUS) versus CT. 27 children were enrolled, with a mean age of 9 years. SonoVue was injected as a bolus followed by a normal saline bolus. 12 patients had 14 abdominal solid organ injuries seen on CT. 13 injuries were identified on CEUS (sensitivity 92.9%, specificity 100%, PPV 100%, NPV 93.8%). No adverse events were reported from contrast administration (10).

Menichini et al reported a retrospective series of 73 children who presented to a single emergency department with concern for an abdominal injury. 67 of the 73 children had an abdominal solid organ injury, only 26 of which were seen on standard ultrasound. Using CEUS with two 1.2 mL doses of SonoVue all 67 solid organ injuries seen on CT were able to be seen for a sensitivity, specificity, PPV and NPV of 100%. No adverse events were noted related to the SonoVue administration (11).

Rosado and Riccabona reviewed the off-label use of intravenous ultrasound contrast in 502 children distributed over 19 published studies (12). The most common agent used was SonoVue, in 447 children, and the second most common reason was to identify abdominal solid organ injuries. Ten patients (2%) were reported to have an adverse event, with 9 of the events being minor and transient. One patient (0.2%) suffered an anaphylactic reaction to the contrast agent and this resolved with proper treatment (12). This adverse event profile compared favorably to that seen with CT contrast (13).

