2. STUDY OBJECTIVES

The primary goal of the study is to evaluate whether the use of ultrasound contrast can improve the sensitivity and specificity of ultrasound in diagnosing abdominal solid organ injuries in pediatric patients, thereby making it a valuable diagnostic tool.

Since all patients entered on the study will have CT positive results, the primary endpoint is the proportion of patients for whom all organs identified by CT with injuries are also identified by CEUS, regardless of injury grade. This will provide an estimate of the sensitivity assuming CT as the gold standard.

The secondary objectives are to determine: 1) for each organ, the proportion of patients for whom the organ is identified by CT and CEUS as injured, 2) proportion of injuries identified by CEUS which are within 1 grade of the injury identified by CT, 3) the proportion of patients where the absence or presence of peritoneal fluid identified by CT is also identified by CEUS, and 4) the comparison between ‘real-time’ and centralized interpretation of CEUS images.

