3. INVESTIGATIONAL PLAN

3.1 OVERALL STUDY DESIGN AND PLAN

To address the primary objective, we propose a multi-center study with participation from 7-10 sites to enroll 132 subjects who complete the study aged 8-17 over 2-3 years. [name] is the Sponsor Investigator, with Boston Children’s Hospital acting as the coordinating center. Prior to enrollment, each subject will have already undergone an abdominal CT that identified at least one solid organ abdominal injury. As part of the study, subjects will undergo a greyscale/Doppler ultrasound and CEUS within 48 hours of injury. The study will measure the number of organ injuries identified, and the severity of organ injury. The ultrasound studies will be performed by a radiologist who is blinded to the results of the CT. The findings on greyscale/Doppler ultrasound and CEUS will be compared to the CT, using the CT findings as the standard.

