3.2 DISCUSSION OF STUDY DESIGN, INCLUDING CHOICE OF CONTROL GROUPS

Children who have an abdominal solid organ injury visualized on abdominal computerized tomography form the study group. Computerized tomography is the current gold standard for the diagnosis of these injuries in children. The purpose for choosing children who have already undergone abdominal computerized tomography is to be able to compare the new imaging technique: contrast enhanced ultrasound, to the gold standard. Children from age 8 through 17 years have been chosen to assure that they are able to assent to the study. At least 1 of the 5 abdominal solid organs (liver, spleen, pancreas, left kidney, right kidney) will be injured per patient and each subject will serve as their own control. CTs will be interpreted by radiologists at the participating institution. Sonographers will be blinded to the results of the computerized tomography.

This study will take place at 7-10 participating institutions. Based on prior data, approximately 30 potentially eligible patients are expected to present at each institution per year. We estimate enrollment will take 2-3 years to enroll 132 subjects who complete the study.

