3.3.3.1 Subject Withdrawal or Early Termination

Subjects could choose to discontinue from the study at any time, for any reason, specified or unspecified, and without prejudice. Subjects could be discontinued from the study for any of the following reasons:

- At the subject's or their parent/guardian's request
- At the discretion of the site Investigator, if deemed appropriate, for any reason, such as the subject's medical status worsening.

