3.3.3.2 Planned Follow-up for Discontinued Subjects

The study has a single phase which lasts 50-90 minutes. We do not anticipate any discontinued subjects.

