3.8.2 Statistical Analysis Plan

We will summarize patient demographic and clinical characteristics using descriptive statistics: means, standard deviations, medians, and ranges for continuous measures; frequencies and proportions for categorical measures. For the primary objective, we will calculate the proportion and 95% confidence interval. For the secondary objectives, we will calculate the proportion and 95% confidence interval. We will also report the sensitivity and specificity of the CEUS relative to CT in identifying individual organ abnormalities in separate models and combined models. In the combined analysis, sensitivity and specificity will be estimated using random effects model or generalized estimating equations to adjust for potential correlation between organs within an individual. Statistical analysis will be performed using standardized packages (SPSS version 19.0 from SPSS Inc./IBM, Chicago, IL or SAS version 9.4 from SAS Institute Inc., Cary, NC.)

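### Does the primary proportion lack a usable denominator because no efficacy analysis set is named?

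*Combined protocol and SAP*

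**What the plan says.** Section 3.8.2 gives the whole primary analysis in one sentence: "For the primary objective, we will calculate the proportion and 95% confidence interval". It does not say over whom.

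The accrual text counts completers. The Synopsis plans for 132 subjects to complete and adds: "Any subjects who do not complete the study will not count toward this number". Section 3.1 plans "to enroll 132 subjects who complete the study", and section 3.2 repeats it: "We estimate enrollment will take 2-3 years to enroll 132 subjects who complete the study". Section 3.8.1 then computes the primary confidence interval with 132 patients.

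Section 2 introduces the endpoint with different words: "Since all patients entered on the study will have CT positive results, the primary endpoint is the proportion of patients". The endpoint, there and in section 3.1.1, is per patient: every organ that CT shows as injured must also be identified by CEUS.

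Section 3.3.3.1 lets subjects withdraw at any time, and lets them be removed "At the discretion of the site Investigator, if deemed appropriate, for any reason". Section 3.3.3.2 says of this single session of 50 to 90 minutes: "We do not anticipate any discontinued subjects".

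Section 3.8.5 names an all-treated set, for safety only. Section 3.8.4 places the interim look after 73 patients without saying whether they are entered, dosed or completed.

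**The concern.** A single-arm study whose main result is one proportion needs a known denominator. Here three can be argued for: everyone entered, everyone dosed, and everyone who completed. The word 'complete' could mean that the second injection was given (section 3.5.2.2) or that the 30-minute observation was also finished (section 3.5.2.3).

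The distinction can touch the endpoint. Under section 3.4.3 the left kidney and spleen are imaged with contrast only after the second injection. If a child with a splenic injury stops after the first injection, the injured organ has not been seen on CEUS. That child is a failure in an all-dosed analysis and absent from a completer analysis. Near 90%, the choice could put the point estimate on either side of the bar, and it could be made after the results are known.

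**Working it through.** **1. Reproduce the plan's figure.** Inputs from section 3.8.1: n = 132, observed proportion 90%, exact two-sided 95% Clopper-Pearson interval.

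- With x = 0.90 × 132 = 118.8, the limits are 83.57% and 94.54%, width 10.97 points. The plan states 83.6%, 94.5% and 11%.
- The smallest whole count reaching 90% is 119: 119/132 = 90.15%, interval 83.7% to 94.7%.

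The interval reproduces with 132, the same number that the Synopsis and sections 3.1 and 3.2 define as completers.

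**2. When do the readings differ?**

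| Event | Entered | Dosed | Completers |
|---|---|---|---|
| Withdraws after consent, before contrast | in | out | out |
| Stops between injections | in | in | out |
| Leaves during the 30-minute observation | in | in | depends on the meaning of 'complete' |
| None of these | in | in | in |

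If nobody falls in the first three rows, all readings give the same number.

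**3. Size, if k dosed subjects do not complete.** Start from 119 successes in 132 completers. The all-dosed estimate is (119 + s)/(132 + k), where s is the number of the k whose CT-injured organs were all identified. It runs from s = 0 (for example, a splenic injury and a stop after the first injection) to s = k (for example, a liver injury already seen).

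| k (assumed) | s = 0 | s = k |
|---|---|---|
| 0 | 119/132 = 90.2% | the same |
| 1 | 119/133 = 89.5% (-0.7) | 120/133 = 90.2% (+0.1) |
| 3 | 119/135 = 88.1% (-2.0) | 122/135 = 90.4% (+0.2) |

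For s = 0 the exact intervals are 83.0% to 94.1% (k = 1) and 81.5% to 93.1% (k = 3), against 83.7% to 94.7% for completers. A subject entered but never dosed, if counted as a failure, has the same arithmetic as s = 0.

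**4. What k is plausible?** The documents give no stop rate. For scale only, section 1.3 describes a pediatric review of 502 children: "Ten patients (2%) were reported to have an adverse event, with 9 of the events being minor and transient". If 2% of dosed exams were stopped, the expected number before the 132nd completer would be 132 × 0.02/0.98 = 2.7. That is an adverse event rate, not a stop rate; most of those events would not end an exam, and stops for other reasons are not covered. It serves only to justify showing k from 0 to 3.

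**5. Interim look.** Section 3.8.4 considers stopping if the chance of a final point estimate of at least 90% is below 10%. Assume the current trend continues over the remaining 132 - 73 = 59 patients.

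- At 64/73, 119 - 64 = 55 more successes are needed: P(Bin(59, 64/73) ≥ 55) = 13.3%.
- At 63/73, 56 are needed: P(Bin(59, 63/73) ≥ 56) = 3.1%.

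One exam matters only at exactly this boundary, and the rule there is to consider stopping, not to stop.

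**The case for a change.** The strongest case for a change is that the denominator should be fixed before results are read, that it costs a few lines, and that at 119/132 one stopped exam with an unidentified injury gives 89.5% in place of 90.2%. Section 3.3.3.1 allows withdrawal, and the expectation in section 3.3.3.2 is not an analysis rule. With more non-completers the gap grows: seven, all counted as failures, would give 119/139 = 85.6%.

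The omission stands, and so does the fact that nothing states how a partial or non-diagnostic CEUS is counted. Three things weaken the rest.

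- The text is less balanced than it looks. The accrual rule and the n in section 3.8.1 together point to completers. The remark in section 2 about patients entered explains why the endpoint estimates sensitivity; it does not define an analysis set. The all-treated set in section 3.8.5 is for safety and says nothing about efficacy.
- Seven non-completers would contradict the plan's own expectation for a single session in hemodynamically stable children, whose ability to finish the procedures within 48 hours of injury is an inclusion criterion in section 3.3.1.
- The 90% line is not a formal patient-level test at the end. Section 3.8.1 refers to the true proportion and sizes the trial on interval precision. The intervals for 119/132 and 119/133 support the same conclusion.

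**Conclusion.** No change to the plan is called for. The efficacy set and the meaning of 'complete' are unstated, but the documents imply completers, and that is a sound choice for the sensitivity of a finished exam. An all-dosed proportion would also be defensible, since it adds feasibility. Neither gives a wrong answer, and both can be computed from data that the study already collects. An analyst would ordinarily report the non-completers and their reasons beside the result.

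The effect is zero if nobody stops. Starting from 119/132, it is -0.7 to +0.1 points for one dosed non-completer and -2.0 to +0.2 for three, against an 11-point interval. These figures rest on assumed counts of 0 to 3 non-completers and on the per-patient endpoint of sections 2, 3.1.1 and 3.8.1; they do not apply to the per-injury wording in the Synopsis and section 3.5.2. The direction depends on which organs are injured and when an exam stops, so no bias is shown. The judgement would need another look if non-completion proved frequent, or if finished but non-diagnostic exams were treated as non-completion.

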3.8.3 Study Duration

To attain the target sample size of 132, we expect to enroll 1-2 patients/month/site across 7-10 sites for enrollment over 2-3 years. The total study duration, including analysis, will be 3-5 years.

3.8.4 Interim Analysis

An interim analysis will be conducted after the first 73 patients. At this time, the conditional power will be calculated. If the probability of obtaining a point estimate $\geq 90\%$ for the primary endpoint is less than 10% at the interim analysis, we will consider stopping the study for futility.

3.8.5 Safety Analysis

All subjects who receive study drug will be analyzed for safety. The proportion of patients with specific adverse events will be reported as well as the worst grade observed across all adverse events. The maximum confidence interval width for these estimates is 17.6%. If the observed estimated adverse event proportion is 10%, the 95% confidence interval is (5.5,16.4%).

3.9 COMPLIANCE STATEMENT

The study will be conducted in accordance with the protocol, Good Clinical Practices, the relevant ICH guidelines, the applicable regulatory requirements, and the ethical principles that have their origins in the Declaration of Helsinki. As required by United States Food and Drug

October 16, 2019

Administration (FDA) Code of Federal Regulations (CFR) (21 CFR 56) and the Declaration of Helsinki, the study protocol, amendments, and Informed Consent form will be reviewed and approved, according to 21 CFR §50 and §56, respectively, by our center's IRB.

3.10 SUBJECT INFORMATION AND CONSENT

The study will be explained to each subject and their guardian and before enrollment in the study, an Informed Consent form will be signed by each subject's guardian and assent will be obtained. A copy of the signed consent form will be given to each guardian.

For any sites that choose to execute an IRB reliance agreement, Boston Children's Hospital Investigational Review Board, as part of the reliance agreement, will provide each site with the informed consent template with prompted areas for each institution's required language. The Sponsor will review the written Informed Consent forms for each study center and submit to BCH IRB (as well as any sites whose IRB maintains local review) for final approval. These documents will meet requirements for subject information, as outlined in FDA regulations (21 CFR 50), ICH Guideline E6, and the Declaration of Helsinki. The Sponsor requires that all subjects be given this information before study participation.

4. COMPENSATION, INSURANCE AND INDEMNITY

There will be no compensation provided for participation in this study.

